1.3. Study AMR-01-01-0017 (ANCHOR Study)

The results from the ANCHOR study are particularly relevant for the dose selection of the present study since the ANCHOR study was conducted in the same patient population. The

primary objective in the ANCHOR study was to determine the efficacy of AMR101 2 g daily and 4 g daily, compared to placebo, in lowering fasting TG levels in patients with high risk for cardiovascular disease (CVD) and fasting TG levels ≥ 200 mg/dL and < 500 mg/dL, despite treatment to low density lipoprotein cholesterol (LDL-C) goal (> 40 mg/dL and < 100 mg/dL) on statin therapy.

After a 6- to 8-week screening period which included diet and lifestyle stabilization, a washout period for excluded non-statin lipid-altering medications (if needed), and a TG qualifying period, patients were randomized to one of 3 treatment groups and received study medication during a 12-week, double-blind treatment period. Patients had to be treated with one of 3 statins (simvastatin, atorvastatin or rosuvastatin) to reach their LDL-C goal of 100 mg/dL (+15% allowed for variability) and had to be on a stable dose for a minimum period of 4 weeks before the TG qualifying measurements. The TG target for enrollment was for patients to have qualifying fasting TG levels of ≥ 200 mg/dL and < 500 mg/dL based on the mean of 2 measurements. During the 12-week double-blind treatment period, patients received orally AMR101 2 g/day, AMR101 4 g/day, or placebo.

In the ITT population (687 patients), the baseline median TG level was 259.0 mg/dL (IQR: 81.00 mg/dL), 264.8 mg/dL (IQR: 93.00 mg/dL) and 254.0 mg/dL (IQR: 92.50 mg/dL) for the patients receiving placebo, AMR101 4 g/day and AMR101 2 g/day, respectively. At the Week 12 endpoint, the median percent change from baseline TG level was +5.9%, -17.5% and -5.6% for the patients receiving placebo, AMR101 4 g/day and AMR101 2 g/day, respectively. The median difference between AMR101 4 g/day and placebo was -21.5% ($p < 0.0001$). The median difference between AMR101 2 g/day was -10.1% ($p = 0.0005$).

The TG lowering effect of AMR101 was similar in males and females at the 4 g/day dose. Efficacy of AMR101 was similar in diabetics and non-diabetics, and was similar irrespective of the type of statin administered. The higher the potency of the statin regimen, the greater the TG reduction in the AMR101 4 g/day group. The higher the baseline TG tertile, the greater the TG reduction for both AMR101 dose groups.

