- Survival analysis using the log-rank test for the primary efficacy outcome comparing the 2 treatment groups (AMR101 and Placebo) and including the stratification factors CV risk category, use of ezetimibe and by geographical region (Westernized, Eastern European, and Asia Pacific countries).
- All statistical analyses for the efficacy and safety outcomes will be performed at the 5% significance level using 2-sided tests unless otherwise noted.
- One interim analysis is planned when approximately 60% of the planned total number of events has occurred.

The analysis is planned to:

- Describe at baseline: Patient characteristics, including lipids and lipoproteins, stroke history, cardiovascular risk factors, diabetes mellitus, or metabolic syndrome, among others.
- Compare the primary, secondary, and tertiary endpoints between treatment groups at the corresponding follow-up time points.

SAMPLE SIZE DETERMINATION:

Sample size estimation is based on the assumption that the primary composite endpoint (time from randomization to the first occurrence of CV death, non-fatal MI, non-fatal stroke, coronary revascularization, or unstable angina requiring hospitalization) would be relatively reduced by 15%, from an event rate by 4 years of 23.6% in the placebo group to 20.5% in the AMR101 group. It is expected that a minimum of 1612 primary efficacy endpoint events will be required during the study. A total of approximately 6990 patients are needed to be able to detect this difference at 4.76% significance level (decreased from 5.00% because of one interim analysis) and with 90% power, assuming an 18-month enrollment period and a median follow-up of 4 years. The current sample size calculation is based on an estimated placebo yearly event rate of 5.9% (23.6% over 4 years). To protect against the possibility that the actual placebo event rate is lower than estimated, an extra 1000 patients will be enrolled (approximately 7990 patients in total). By adding the extra 1000 patients, the event rate in the placebo group could be 5.2% per year (20.8% over 4 years) without having to modify the other sample size assumptions.

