- To assess the effects regarding lipids, lipoproteins and inflammatory markers including triglycerides (TG), total cholesterol (TC), low-density lipoprotein cholesterol (LDL-C), high-density lipoprotein cholesterol (HDL-C), non-HDL-C, very low-density lipoprotein cholesterol (VLDL-C), apolipoprotein B (apo B), high sensitivity C-reactive protein (hs-CRP) and high sensitivity troponin (hsTnT), as follows:
 - Assessment of the effect of AMR101 on each marker (on-treatment change of markers)
 - Assessment of the effect of the baseline value of each marker on treatment effects (baseline effect on outcomes)
 - To evaluate the effect of therapy for preventing clinical events, as defined above, among all patients in the study, and in subgroups such as patients with diabetes mellitus and patients with substantial on-treatment changes of any of the markers (on-treatment effect on outcomes).
- To evaluate the effect of therapy on new onset diabetes (See appendix C);
- To explore the effect of AMR101 on weight and waist circumference.

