12.2.4.2. Primary Endpoint

The primary efficacy endpoint is the time from randomization to the first occurrence of any component of the composite of the following clinical events:

- CV death,
- Nonfatal MI (including silent MI),
- Nonfatal stroke,
- Coronary revascularization,
- Hospitalization for unstable angina determined to be caused by myocardial ischemia by invasive/non-invasive testing.

The analysis of the primary efficacy endpoint will be performed using the log-rank test comparing the 2 treatment groups (AMR101 and placebo) and including the stratification factor “CV risk category”, use of ezetimibe and geographical region (Westernized, Eastern European, and Asia Pacific countries) (each as recorded in the IWR at the time of

enrollment) as covariates. Treatment difference will be tested at alpha level of 0.0476 accounting for one interim efficacy analysis. The hazard ratio for treatment group (AMR101 vs. placebo) from a Cox proportional hazard model that includes the stratification factor will also be reported, along with the associated 95% confidence interval. Kaplan-Meier estimates from randomization to the time to the primary efficacy endpoint will be plotted.

The size and direction of the treatment effects of the individual components of the composite endpoint and their relative contribution to the composite endpoint will be determined as well.

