12.2.4.5. Exploratory Subgroup Analyses

Subgroup analyses of the primary and key secondary endpoints (as defined in the Statistical Analysis Plan) will be performed. All subgroup analyses will be conducted for the ITT population. No adjustments for multiple testing will be made.

Log-rank tests, treatment effects and the associated 95% confidence intervals for the primary and key secondary efficacy endpoints within each subgroup will be provided using the Cox proportional hazard model with treatment (AMR101 or placebo), and stratification as a factor (with the exception of the subgroup analyses of those subgroup variables related to the stratification factors, i.e., CV risk category that will not have stratification as a factor).

Subgroups including, but not limited to the following, will be explored. A complete list will be prospectively defined in the Statistical Analysis Plan.

Demographics:

- Gender,
- age (<65 yr and ≥65 yr),
- race (white and nonwhite, or any other subset with at least 10% of the total number of patients),
- geography (western vs. non-western)

Disease Parameters:

- CV risk category,
- the presence/absence of diabetes at baseline,
- renal impairment

Treatment Parameters:

- by statin intensity (statin type and regimen),
- relevant concomitant medications,

Baseline Lipid and Lipoprotein Parameters:

- LDL-C (by tertile),
- HDL-C (by tertile),
- TG (by tertile),
- TG ≥150 mg/dL,
- TG ≥200 mg/dL and TG <200 mg/dL,
- combined highest tertile for TG and lowest tertile for HDL-C,
- hs-CRP (≤3 mg/L and >3 mg/L),
- Apo B (by tertile),
- non-HDL-C (by tertile)

The consistency of the treatment effects in subgroups will be assessed for the primary and key secondary efficacy endpoints. For each subgroup variable, a Cox proportional hazard model with terms for treatment, stratification factors (with the exception of those subgroup variables related to the stratification factors, i.e., CV risk category), subgroup, and treatment-by-subgroup interaction will be performed. The main treatment effect will not be tested with this model. P-values for testing the interaction terms will be provided.

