12.3. Sample Size Determination

Sample size estimation is based on the assumption that the primary composite endpoint (time from randomization to the first occurrence of CV death, non-fatal MI, non-fatal stroke, coronary revascularization, or unstable angina requiring hospitalization) would be relatively reduced by 15%, from an event rate by 4 years of 23.6% in the placebo group to 20.5% in the AMR101 group. It is expected that a minimum of 1612 primary efficacy endpoint events will be required during the study. A total of approximately 6990 patients are needed to be able to detect this difference at 4.76% significance level (because of the interim analysis described in Section 12.2.4.6) and with 90% power, assuming an 18-month enrollment period and a median follow-up of 4 years. The current sample size calculation is based on an estimated placebo yearly event rate of 5.9% (23.6% over 4 years). To protect against the possibility that the actual placebo event rate is lower than estimated, an extra 1000 patients will be enrolled (approximately 7990 patients in total). By adding the extra 1000 patients, the event rate in the placebo group could be 5.2% per year (20.8% over 4 years) without having to modify the other sample size assumptions.

Since this is an events-driven trial, the ‘sample size’ is the number of events rather than the number of patients. The number of events that occur depends primarily on three factors: how many patients are enrolled, the combined group event rate, and how long the patients are followed. Because of the difficulty in predicting the combined event rate, the sponsor will monitor that event rate as the trial progresses. If the combined event rate is less than anticipated, either increasing the number of patients, extending the length of follow-up, or a balance of adjusting both factors may be necessary to achieve the sample size of 1612 events.

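### No interaction of treatment with baseline TG or the other markers on a continuous scale is specified beside the tertile and threshold subgroups; adding one is cheap and gains power if the effect is graded

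*Combined protocol and SAP*

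**What the plan says.** Section 2 of Amendment 1 lists a tertiary objective: "Assessment of the effect of the baseline value of each marker on treatment effects (baseline effect on outcomes"). Section 9.2.3 carries a matching endpoint, the effect of baseline and on-treatment change of biomarkers on the primary and key secondary endpoints. Neither mentions a cut. Section 12.2.4.4 gives rank-based methods for comparing marker changes between arms, but no model for effect modification.

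The model is in Section 12.2.4.5. For each subgroup variable it fits a Cox model with treatment, the stratification factors, the subgroup and their interaction, and "P-values for testing the interaction terms will be provided". LDL-C, HDL-C, TG, apo B and non-HDL-C are listed by tertile. TG also has fixed limits at 150 and 200 mg/dL, hs-CRP is split at 3 mg/L, and one group is the "combined highest tertile for TG and lowest tertile for HDL-C". The section does not say whether a tertile interaction is tested as unordered classes (2 df) or as a trend (1 df). It is labelled exploratory, makes no multiplicity adjustment, describes its list as not exhaustive, and leaves the full list to the SAP.

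Total cholesterol, VLDL-C and hsTnT are named in the objective and endpoint but do not appear in that list.

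**The concern.** The markers are measured on continuous scales at the randomization visit. Cutting one into three groups discards the variation within each group, and an unordered 2-df test also discards the order of the groups. If benefit rises or falls gradually with baseline TG, a grouped test is more likely to return a non-significant interaction, and that result is easily read as a consistent effect. Tertile edges also depend on the sample, so a tertile hazard ratio does not belong to a stated TG level, although the two fixed TG limits partly answer that.

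A gradient is at least plausible on the documents' own terms. Section 1.5 of Amendment 1 cites a post hoc analysis of a statin trial in which risk fell by 2.3% for each 10% lowering of TG.

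**Working it through.** **Inputs from the documents.** 1612 primary events and 90% power ("with 90% power, assuming an 18-month enrollment period", Section 12.3); a 15% relative reduction ("relatively reduced by 15%, from an event rate by 4 years of 23.6"%, same section), taken as HR 0.85; 1:1 allocation (synopsis); "Treatment difference will be tested at alpha level of 0.0476" for the primary endpoint (Section 12.2.4.2); and "5% significance level using 2-sided tests unless otherwise noted" for other analyses (Amendment 1 synopsis).

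**The plan's own figure.** Schoenfeld's formula gives D = 4 × (z₀.₉₇₆₂ + z₀.₉₀)² / (ln 0.85)² = 1612, so the event target is reproduced. The documents state no interaction power.

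**Assumptions not in the documents.** The marker is roughly normal on a suitable scale, the treatment log-HR is linear in it, and the slope is b per standard deviation. The size of b is unknown, so a range is shown.

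**Continuous test.** With 1:1 allocation the non-centrality is b² × D/4 = 403 × b², on 1 df. For b = 0.10 it is 4.03, which gives 51.9% power.

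**Share of information kept after cutting.**
- Tertiles: the tertile means of a standard normal are −1.091, 0 and +1.091, so the between-group share is (2/3) × 1.091² = 0.793. For TG taken as log-normal (median 220 mg/dL, log-SD 0.35, truncated to 135-500 mg/dL, all assumed) the share is 0.83.
- Median cut: 2/π = 0.637.
- Cut at percentile p: φ(z_p)² / [p(1−p)], which is 0.595 at the 67th, 0.539 at the 75th and 0.490 at the 80th.

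Multiplying the non-centrality by the share gives the power at 1612 events, two-sided 0.05. Tertile hazard ratios are 0.85 × exp(±1.091b) in the outer tertiles.

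| b per SD | Tertile HRs | Continuous, 1 df | Tertile classes, 2 df (share 0.79 / 0.83) | Tertile trend, 1 df (0.79) | Median cut, 1 df |
|---|---|---|---|---|---|
| 0.075 | 0.92 / 0.85 / 0.78 | 32.5% | 20.6% / 21.4% | 26.8% | 22.5% |
| 0.10 | 0.95 / 0.85 / 0.76 | 51.9% | 34.0% / 35.4% | 43.2% | 36.0% |
| 0.125 | 0.97 / 0.85 / 0.74 | 70.9% | 50.3% / 52.3% | 60.8% | 51.7% |
| 0.14 | 0.99 / 0.85 / 0.73 | 80.2% | 60.4% / 62.5% | 70.6% | 61.1% |
| 0.15 | 1.00 / 0.85 / 0.72 | 85.3% | 66.8% / 68.9% | 76.5% | 67.1% |

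The 2-df loss runs from 32.5 − 21.4 = 11.1 points to 70.9 − 50.3 = 20.6 points. The trend loss runs from 32.5 − 26.8 = 5.7 to 70.9 − 60.8 = 10.1. Where the continuous test has 80% power, a single cut loses 22.0 points at the 67th percentile, 26.2 at the 75th and 30.0 at the 80th.

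**Simulation check.** In 1000 simulated trials (7990 patients, about 1650 events, the truncated log-normal TG), continuous against 2-df tertile power was 52.1% against 35.3% at b = 0.10 and 71.0% against 52.2% at b = 0.125. With no interaction the rejection rates were 4.2% and 5.5%.

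**Counter-case.** If the true modification is a step at the upper tertile edge, a linear term captures 0.595 of the information. When the 2-df tertile test has 80% power (non-centrality 9.63), the linear test has non-centrality 9.63 × 0.595 = 5.73 and 66.8% power. At 90% (12.65) it has 7.53 and 78.3%. The linear test is then 13.2 and 11.7 points weaker, and it has essentially no power against a symmetric U-shape.

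**The case against.** A reader might infer that the plan tests these markers only in grouped form. The documents do not support that. The tertiary objective and endpoint are stated without a cut and without a method, the subgroup list is open, and the full list is deferred to the SAP. The text supplied ends at the title page of Amendment 2 and contains no SAP. What can be said is that no continuous interaction is specified in the text supplied.

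A reader might also take one figure, such as 16-19 points, as the cost of this plan. That figure is one scenario: a linear effect, a moderate slope and unordered tertile classes. The coding is not stated, a trend coding roughly halves the loss, and a step reverses it.

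The evidence for a gradient is limited. The statement that the higher the baseline TG tertile, "the greater the TG reduction for both AMR101 dose groups", stands in Section 1.3 of the original protocol, was not carried into Amendment 1, and concerns TG lowering, not cardiovascular events. The 2.3% figure concerns achieved TG lowering, not baseline TG. Section 1.5 also says that pleiotropic effects may contribute and that a modest TG decrease could still bring benefit, which would weaken any dependence on baseline TG.

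The cuts have reasons too: 200 mg/dL is the Amendment 1 entry limit, 150 mg/dL was the original target, hs-CRP above 3 mg/L is a risk-category criterion, and a high-TG, low-HDL-C group has a precedent in the Japanese ethyl-EPA trial cited in Section 1.5. These points are good grounds for keeping the grouped analyses. They do not count against adding a continuous test.

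**Conclusion.** This is a cheap improvement, not an error. The only interaction model specified for baseline lipid and inflammatory markers in the text supplied uses cut markers, and the analyses of baseline marker value in Sections 2 and 9.2.3 have no stated model. Under a graded effect, every grouped coding examined loses power: about 11-21 points for 2-df tertiles, about 6-10 for a tertile trend, and up to about 30 for an off-median single cut. These sizes rest on an assumed normal marker, a linear log-HR and slopes for which the continuous test has about 32-85% power. Under a step at the upper tertile the tertile test is better by about 12-13 points, so neither form dominates and both should be reported. The analyses are exploratory and unadjusted, so the primary test and its alpha are unaffected.

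**What to change.** In Section 12.2.4.5 and the SAP, before unblinding, add for each continuous baseline marker a prespecified 1-df interaction of treatment with the marker as a continuous covariate, on the log scale for TG and hs-CRP, in the same Cox model with the stratification factors. Add a plot of the treatment hazard ratio against the marker from a restricted cubic spline with 3 knots. Keep the tertile, threshold and combined TG/HDL-C subgroup estimates and their interaction p-values. It would also help to state whether tertile interactions are tested on 2 df or as a trend.

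The cost is SAP wording and a few model runs on data already collected. The downside is some extra exploratory tests and a linear term that is less sensitive to a step or a U-shape; the retained tertiles and the spline would show such a pattern.

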12.2.4.6. Interim Efficacy Analysis

One interim analysis will be performed for the primary efficacy endpoint using best available data (adjudicated events and site reported endpoints) based on data when approximately 60% of the total number of primary endpoint events is reached. The interim analysis will be based on a group sequential design that includes early stopping rules for benefit while preserving the overall Type I error rate (O'Brien-Fleming). This allows for interim analysis and preserves the overall Type I error probability of $\alpha=0.05$ for the primary endpoint.

Approximately 1612 primary efficacy endpoint events are planned to be observed during the trial, based on sample size calculation assumptions. Therefore, the interim analysis will occur after at least 967 primary efficacy endpoint events have been observed. According to this

boundary, the critical p-value at the interim analysis has to be $p \leq 0.0076$, resulting in the final evaluation p-value of 0.0476.

The interim results of the study will be monitored by an independent DMC. The analyses will be performed by the independent statistical group unblinded to the treatment assignment. The results will be reported only to the DMC. The unblinded information will not be released to sponsor under any circumstance before the completion of the study. Specific statistical guidelines for data monitoring will be discussed and formalized in a separate Interim Statistical Analysis Plan and DMC Charter.

12.2.5. Analysis of Safety

All analyses of safety will be conducted on the safety population, which is defined as all randomized patients who receive at least one dose of study drug. The safety assessment will be based on the frequency of adverse events, physical exams, vital signs and safety laboratory tests.

Adverse events with new onset during the study between the initiation of study drug and 30 days after the last dose of study drug for each patient will be considered treatment-emergent (TEAEs). This will include any AE with onset prior to initiation of study drug and increased severity after the treatment initiation.

Treatment-emergent adverse events will be summarized by system organ class and preferred term, and by treatment. This will include overall incidence rates (regardless of severity and relationship to study drug), and incidence rates for moderate or severe adverse events. A summary of SAEs and adverse events leading to early discontinuation from the study will be presented through data listings.

Safety laboratory tests and vital signs will be summarized by post-treatment change from baseline for each of the parameters using descriptive statistics by treatment group. Those patients with significant laboratory abnormalities will be identified in data listings. Additional safety parameters will be summarized in data listings.

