12.2.5. Analysis of Safety

All analyses of safety will be conducted on the safety population, which is defined as all randomized patients who receive at least one dose of study drug. The safety assessment will be based on the frequency of adverse events, physical exams, vital signs and safety laboratory tests.

Adverse events with new onset during the study between the initiation of study drug and 30 days after the last dose of study drug for each patient will be considered treatment-emergent (TEAEs). This will include any AE with onset prior to initiation of study drug and increased severity after the treatment initiation.

Treatment-emergent adverse events will be summarized by system organ class and preferred term, and by treatment. This will include overall incidence rates (regardless of severity and relationship to study drug), and incidence rates for moderate or severe adverse events. A summary of SAEs, and adverse events leading to early discontinuation from the study will be presented through data listings.

Safety laboratory tests and vital signs will be summarized by post-treatment change from baseline for each of the parameters using descriptive statistics by treatment group. Those patients with significant laboratory abnormalities will be identified in data listings. Additional safety parameters will be summarized in data listings.

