There is a growing body of evidence, encompassing molecular, cellular, animal and human studies defining the roles for O3FAs as bioactive agents for reducing the risks of and treating CVD (Torrejon 2007). Many epidemiological studies have demonstrated inverse associations between fish intake and CV mortality, and more specifically between the intake and blood levels of O3FAs and CV mortality. For example, when comparing blood levels of O3FAs among men who had died of sudden cardiac death with controls matched for age and smoking status, it was found that participants with the highest blood levels of EPA and DHA had a 90% risk reduction for sudden cardiac death compared with those with the lowest levels (Albert 2002).

Clinical trials and experimental studies, suggest important antiatherogenic and antithrombotic effects of O3FAs. These result from wide-ranging biological effects, including benefits on lipoprotein metabolism, blood pressure, endothelial function and vascular reactivity, inflammation, platelet and fibrinolytic function, cytokine production, coagulation and oxidative stress (Mori and Woodman 2006). Evidence suggests that increased consumption of O3FAs from fish or fish-oil supplements reduces the rates of all-cause mortality, cardiac and sudden death, and possibly stroke (Wang 2006). The effect was evident in both primary-prevention (general population without a history of CVD) and secondary-prevention (patients with a history of CVD) studies with a stronger effect in secondary prevention.

The Diet and Reinfarction Trial (DART) was one of the first randomized, controlled studies to demonstrate the beneficial effects of O3FAs in secondary prevention of CHD and reported a 29% reduction in all-cause mortality over a 2-year period in 2033 male MI survivors advised to increase their intake of oily fish (200 to 400 g of fatty fish per week, which provided 500 to 800 mg/day of O3FAs) (Burr 1989). While not statistically significant, there was also a trend toward a reduction in recurrent ischemic heart disease events with increased fatty fish consumption. A post hoc analysis of patients receiving fish oil capsules (900 mg/day of EPA+DHA) in DART suggested that the protective effect was attributable to O3FAs (Burr 1994). The greatest benefit was seen in fatal MIs, and this observation led to the hypothesis that O3FAs might protect the myocardium against the adverse sequela of acute ischemic stress.

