1.6. Risk/Benefit

Across all completed Amarin-sponsored studies, the proportion of patients (based on the safety population from the randomized, double-blind periods of the studies) experiencing any adverse events was similar for patients on placebo (light paraffin oil) and patients on AMR101 (57.1% and 57.4% for placebo and AMR101, respectively). The proportion of patients experiencing a serious adverse event (SAE) was also similar for both treatment groups (5.2% and 6.0% for placebo and AMR101, respectively). The safety profile in the open-label extensions was similar to that observed in the double-blind treatment periods. There were no SAEs attributed to AMR101 during the open-label extension periods of the studies.

In summary, AMR101 is very well tolerated at daily doses up to 4 g. The side effects reported by the patients taking AMR101 were generally similar to those reported by the patients taking placebo. Ethyl-EPA is a pro-drug, and is rapidly and completely hydrolyzed to EPA. EPA is a natural substance found universally as a component of all cell membranes. It is classified as an essential fatty acid. Because of the nature of EPA, as an essential component of normal tissue and its part in normal metabolism, human studies have demonstrated that it is safe. See the Investigator's Brochure for more information.

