Patients whose treatment with study medication is discontinued early, and have not withdrawn consent, will stay in study and will be monitored until the end of the study. Patients that continue in the study after indefinite cessation of therapy will be characterized as Off Drug In Study (ODIS). ODIS patients should be asked to return to the study site for an interim visit once the patient has been off study drug for >30 days. Procedures at this visit are consistent with those at Visit 5. If not contraindicated, patients will also have the option to restart study medication at any point once characterized as ODIS.

The reason for study drug discontinuation or interruption will be recorded on the CRF.

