12.2.1. Patient Disposition and Demographic/Baseline Characteristics

The numbers of patients screened, the number of patients randomized per treatment group (randomized population), and the number of patients in the ITT and PP populations by treatment group will be listed.

For randomized patients who discontinued treatment with study drug, the primary reason for discontinuation will be listed and summarized by treatment group.

Summary statistics (mean, standard deviation, median, minimum and maximum) will be provided by treatment group for demographic characteristics (e.g., age, sex, race, and ethnicity) and baseline characteristics (e.g., body weight, height, and body mass index) in the ITT and PP populations.

Demographic data and baseline characteristics will be compared among treatment groups for the ITT and PP population. Differences in demographic and baseline characteristics will be tested using a chi-square test (for categorical variables) or a 1-way analysis of variance model with treatment as a factor (for continuous variables). The p-values will be used as descriptive statistics, primarily as an assessment of the adequacy of randomization.

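### The protocol through Amendment 1 plans no by-arm incidence table of serious adverse events, and none by term of the adverse events that stopped study drug

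*Combined protocol and SAP*

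**What the plan says.** Section 12.2.5 of Amendment 1 sets out the adverse-event analysis in two steps. The first is tabular and by arm: "Treatment-emergent adverse events will be summarized by system organ class and preferred term, and by treatment". It covers overall incidence and "incidence rates for moderate or severe adverse events". The second is not tabular: "A summary of SAEs and adverse events leading to early discontinuation from the study will be presented through data listings". The original protocol has the same plan in its own section 12.2.5.

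Four other places in Amendment 1 bear on this:

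- **Section 11.1** on stopping drug: "Patients whose treatment with study medication is discontinued early, and have not withdrawn consent, will stay in study". These patients are labelled Off Drug In Study (ODIS), and the reason for stopping is recorded on the CRF. Section 11.2 requires follow-up of all randomized patients to the study end date or death.
- **Section 12.2.1**: "For randomized patients who discontinued treatment with study drug, the primary reason for discontinuation will be listed and summarized by treatment group".
- **Section 10.2.1**: endpoint events are recorded for endpoint determination and are not captured as SAEs.
- **Section 1.6**: the proportions of patients with an SAE in earlier sponsor studies are compared by arm, "5.2% and 6.0% for placebo and AMR101, respectively".

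**The concern.** Section 12.2.5 changes its form of presentation just where the events become more important. All adverse events receive incidence rates by treatment; serious ones receive a listing, from which a reader must count patients by hand to obtain a rate. Section 10.2.1 sharpens this. Once endpoint events are taken out, the SAE set is the serious harm that the efficacy analysis does not examine, apart from deaths, which total mortality covers.

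The discontinuation listing has a second problem. It follows adverse events that led patients out of the study, but the design is built to keep patients in the study after they stop drug. Read literally, it would omit most adverse events that ended treatment.

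At stake is the risk side of the benefit-risk conclusion. Section 1.6 argues the safety of the drug from a by-arm SAE comparison in earlier studies. The present trial, with about 7990 patients and a planned median follow-up of 4 years, specifies no equivalent.

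**Working it through.** The plan gives no figure for this point, so the check is mainly of the text.

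**Step 1. What is compared by arm, and what is not (Amendment 1).**

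| Question | Planned by-arm analysis | Section |
|---|---|---|
| Any treatment-emergent adverse event | Yes, by system organ class and preferred term | 12.2.5 |
| Moderate or severe events | Yes | 12.2.5 |
| Primary reason for stopping drug | Yes, one reason per patient | 12.2.1 |
| Total mortality and CV endpoints | Yes, log-rank | 12.2.4.2 to 12.2.4.4 |
| Treatment-emergent SAEs | No, listing only | 12.2.5 |
| Adverse events leading to stopping drug, by term | No; the listing concerns leaving the study | 12.2.5 |

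**Step 2. Does the moderate-or-severe table stand in for an SAE table?** No. Section 10.2 grades severity by interference with normal activities. Section 10.2.1 defines seriousness by outcome: death, threat to life, hospitalization, disability and so on. Serious events are inside the by-arm tables but cannot be separated from the rest.

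**Step 3. Does the summary of reasons stand in for a table by term?** Only in part. It should give the number per arm who stopped because of an adverse event, since section 11.1 lists that as a reason. It does not show which events those were.

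**Step 4. What an SAE table would deliver.** Inputs: 3995 per arm (section 3.6); earlier-study proportions of 5.2% and 6.0% (section 1.6); and, as an assumption, higher rates in both arms up to 30%, because this trial is longer than the earlier ones.

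Half-width of the 95% CI for the difference = 1.96 × √[p₁(1−p₁)/n + p₂(1−p₂)/n]

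- 5.2% and 6.0%: 1.96 × √[(0.0493 + 0.0564)/3995] = 1.96 × 0.00514 = 0.0101, or 1.0 point. Expected patients: 3995 × 0.052 ≈ 208 and 3995 × 0.060 ≈ 240. An observed difference of 0.8 points would have a CI of about −0.2 to +1.8.
- 10% in both arms (assumed): 1.96 × √(0.18/3995) = 0.0132, or 1.3 points.
- 20% in both arms (assumed): 1.96 × √(0.32/3995) = 0.0175, or 1.8 points.
- 30% in both arms (assumed): 1.96 × √(0.42/3995) = 0.0201, or 2.0 points.

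The listing as planned yields no such estimate.

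**The case against.** The strongest reply is that the arms are far from uncompared. All treatment-emergent events are tabulated by treatment. The reason for stopping drug is summarized by treatment. Total mortality and fatal and nonfatal stroke are tested as secondary endpoints, and CV mortality, hospitalized arrhythmia and cardiac arrest are analyzed as tertiary ones. The DMC also reviews safety (section 5.4). All of this stands. A reader might infer from section 12.2.5 alone that the trial never compares the arms on serious harm or on treatment-stopping events; the documents do not support that.

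Second, section 12.2 defers detailed methods to a separate SAP, and a second amendment followed. Neither the SAP text nor the body of Amendment 2 was available, so the tables may exist there. That limits the point to the protocol through Amendment 1. It does not remove it, because section 12.2.5 is not silent: it names listings as the form of presentation.

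Third, section 11.1 itself mentions a request to discontinue from the study among the reasons for stopping drug, so the wording of 12.2.5 may simply be loose. That is fair. The discontinuation half is then a wording correction, but the missing by-arm table remains.

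Fourth, the earlier SAE rates do not transfer directly. The sponsor's CNS trials had double-blind periods of 6 weeks to 1 year (section 1.2), and this trial removes endpoint events from SAEs. This too is fair, and is why a range is shown.

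A reader might also infer that a pooled bleeding analysis is required, because section 1.5 says that studies "suggest important antiatherogenic and antithrombotic effects of O3FAs". The documents present this as a benefit and do not name bleeding as an expected harm. Section 1.5 reports no difference in recurrent hemorrhagic cerebral events in the large Japanese ethyl-EPA trial. That inference is not part of this point.

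**Conclusion.** The point holds in a limited form. As written through Amendment 1, the plan produces no by-arm incidence of treatment-emergent, non-endpoint SAEs and no by-arm table by term of the adverse events that led to stopping study drug, and its discontinuation listing is tied to the wrong event. Nonfatal serious harm outside the endpoints is therefore contained in the general tables but never shown separately by arm. The precision forgone is an SAE difference known to about ±1.0 point at the earlier-study rates and about ±2.0 points at an assumed 30%, given 3995 per arm. Those rates are illustrative; the textual gap does not depend on them. The primary efficacy test is unaffected. The change is worth making because it is cheap and improves the safety conclusion, subject to what the SAP and Amendment 2 may already contain.

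**What to change.** In section 12.2.5, or the matching SAP section:

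1. Reword the discontinuation item so that it refers to adverse events leading to discontinuation of study drug.
2. Add by-arm tables, by system organ class and preferred term, with counts and percentages of patients, for (i) treatment-emergent SAEs and (ii) treatment-emergent adverse events leading to discontinuation of study drug. For each, give the overall risk difference with its 95% CI.
3. State in the SAE table that endpoint events are excluded under section 10.2.1.
4. Keep the listings as supporting material.

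The cost is one changed phrase and a few extra tables. SAEs and reasons for stopping drug are already collected, so no new visits or procedures are needed.
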